## 6.3. Windowing Conventions

All assessments, including unscheduled assessments, will be allocated to analysis visit window. Tables and listings will be based on analysis window defined below and the schedule in section 1.3 of the protocol. Allocations of assessments will be performed using their relative day and only for the scheduled visit windows.

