### Non-efficacy Analysis Visit Definition

	Target Day Assigned Study Day (Inclusive)		Day (Inclusive)	Week Assigned
		From	То	
Treatment	1		1ª	Baseline
	8	1 b	11	Week 1
	15	12	18	Week 2
	22	19	25	Week 3
•	29	26	32	Week 4
•	36	33	39	Week 5
	43	40	46	Week 6
	50	47	53	Week 7
	57	54	60	Week 8
	57 + (x*7)	57 + (x*7) - 3	57 + (x*7) + 3	Week 8+x °
Safety Follow- up	Final dose + 56 days	(Final dose + 56 days ) - 3 days	(Final dose + 56 days ) + 3 days	Week xx+ 56 days

<sup>a Last available non-missing measurement from the parent study 2104.

Note: After treatment period ends, safety follow-up will be of approximately 8 weeks (56 days  $\pm$  3 days) . Some parameters which are not collected at every visits, visit window will be combined (by extending window with previous or subsequent visits).

Document: BIOSdata\argenx\Efgartigimod\HAB40220\Biostatistics\Documentation\SAP

Author: Version Number: 1.0

Version Date: 03 June 2024

Template No.: CS\_TP\_BS016 Revision 7 Reference: CS\_WI\_BS005

<sup>b Post baseline visit Day 1.

c considers value of x, starting from 1 to up until 40 to get visit windows for Week 9 to Week 48.

Page 19 of 54

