### Serum Checmistry and hematology, Physical examination, Analysis Visit Definition

	Target Day	Assigned Study Day (Inclusive)		Week Assigned
		From	То	
Treatment	1		1 a	Baseline
	29	1 b	57	Week 4
	85	58	127	Week 12
	169	128	253	Week 24
	337	254	340	Week 48
Safety Follow- up	Final dose + 56 days	(Final dose + 56 days ) - 3 days	(Final dose + 56 days ) + 3 days	Week xx+ 56 days

<sup>a Last available non-missing measurement from the parent study 2104b Post baseline visit Day 1.

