### **Efficacy Analysis Visit Definition**

For MAPS efficacy assessments, the following window will be considered:

Target Day	Assigned Str	ıdy Day (Inclusive)	Week Assigned
	From	То	
1		1	Baseline
15	2	22	Week 2
29	23	36	Week 4
43	37	50	Week 6
57	51	64	Week 8
71	65	78	Week 10
85	79	99	Week 12
113	100	127	Week 16
141	128	155	Week 20
169	156	211	Week 24
253	212	295	Week 36
337	296	340	Week 48

Last available non-missing measurement from the parent study 2104

For COMPAS efficacy assessments, the following window will be considered:

Target Day	Assigned Study Day (Inclusive)	
------------	--------------------------------	--

Document: BIOSdata\argenx\Efgartigimod\HAB40220\Biostatistics\Documentation\SAP

Author: Version Number: 1.0

Version Date: 03 June 2024

Template No.: CS\_TP\_BS016 Revision 7 Reference: CS\_WI\_BS005

	From	То	Week Assigned
1		1	Baseline
15	2	22	Week 2
29	23	43	Week 4
57	44	71	Week 8
85	72	127	Week 12
169	128	211	Week 24
253	212	295	Week 36
337	296	340	Week 48

Last available non-missing measurement from the parent study 2104

For PGI-S, PGI-C and PROMIS Fatigue efficacy assessments, the following window will be considered:

Target Day	Assigned St	udy Day (Inclusive)	Week Assigned
	From	To	
1		1	Baseline
15	2	22	Week 2
29	23	57	Week 4
85	58	106	Week 12
169	149	178	Week 24
337			Week 48

Last available non-missing measurement from the parent study 2104

For PROMIS Cognition efficacy assessments, the following window will be considered:

Target Day	Assigned Study Day (Inclusive)		Week Assigned
	From	To	
1		1	Baseline
29	2	57	Week 4
85	58	127	Week 12
169	128	253	Week 24

Document: BIOSdata\argenx\Efgartigimod\HAB40220\Biostatistics\Documentation\SAP

Author: Version Number: 1.0

Version Date: 03 June 2024

Template No.: CS\_TP\_BS016 Revision 7 Reference: CS\_WI\_BS005

Page 22 of 54

337	254	240	Week 48
-----	-----	-----	---------

Last available non-missing measurement from the parent study 2104

Target Day	Assigned Study Day (Inclusive)		Week Assigned
	From	То	
1		1ª	Baseline
85	1 b	127	Week 12
169	128	253	Week 24
337	254	340	Week 48

<sup>a Last available non-missing measurement from the parent study 2104

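### Seven of the eight printed Week 48 windows in SAP 6.3 close on day 340, so a value 4 or more days late leaves the Week 48 by-visit summaries; the eighth (PROMIS Cognition) is impossible as printed

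*SAP*

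**What the plan says.** SAP 6.3 (Windowing Conventions) opens with a commitment that "All assessments, including unscheduled assessments, will be allocated to analysis visit window". It then restricts this: "Allocations of assessments will be performed using their relative day and only for the scheduled visit windows".

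The Week 48 limits appear in several tables of that section:

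- **Generic non-efficacy table:** target 57 + 7x, ±3 days, where the footnote "considers value of x, starting from 1 to up until 40 to get visit windows for Week 9 to Week 48".
- **Chemistry/hematology/physical examination:** the row reads "337 254 340 Week 48" (target, from, to). The immunogenicity table, the ECG table and one table without a visible label carry the same limits.
- **MaPS and COMPASS 31:** both rows read "337 296 340 Week 48".
- **PROMIS Cognition:** the row reads "337 254 240 Week 48".

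The table for PGI-S, PGI-C and PROMIS Fatigue shows no Week 48 limits in the text available. That may be a reading artefact, so I do not count it.

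Within a window the SAP uses the recorded value nearest the target day. SAP 7.1 and 15.1.1 impute no missing efficacy values. Protocol 9.3.1 assigns visits from actual dates, so a visit's nominal label does not rescue it. Protocol Table 1 allows ±2 days around each scheduled visit.

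**The concern.** An analysis window exists to absorb visits that miss their date. Here the last window on treatment absorbs almost no lateness but a great deal of earliness. A completer whose Week 48 questionnaires fall on day 341 contributes nothing to the Week 48 summary. A participant with an unscheduled, IMP discontinuation or early discontinuation assessment on day 300 can count as Week 48.

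Week 48 is one of the two endpoint visits named for every secondary efficacy outcome (Protocol Section 3), and about 38 participants are expected. The two opening sentences of SAP 6.3 also cannot both be followed once a value falls between windows. The PROMIS Cognition row is a separate error in the same tables: taken literally, it leaves that endpoint with no Week 48 data at all.

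**Working it through.** **Reproduce the SAP's own figures.** Week 48 target = 48×7 + 1 = 337, which equals 57 + 40×7. The generic window with x = 40 is 337 − 3 = 334 to 337 + 3 = 340.

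**Tolerance on each side of day 337** (days early = 337 − from; days late = to − 337):

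| Week 48 window | From–to | Days early | Days late | Day 341 |
|---|---|---|---|---|
| Generic non-efficacy | 334–340 | 3 | 3 | out |
| Chemistry/hematology/physical examination | 254–340 | 83 | 3 | out |
| Immunogenicity | 254–340 | 83 | 3 | out |
| ECG | 254–340 | 83 | 3 | out |
| Unlabelled table | 254–340 | 83 | 3 | out |
| MaPS | 296–340 | 41 | 3 | out |
| COMPASS 31 | 296–340 | 41 | 3 | out |
| PROMIS Cognition, as printed | 254–240 | – | – | out; day 337 also out |

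So seven of eight close on day 340, six of those seven are asymmetric, and one of the eight is empty.

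**Where the next window starts.** The follow-up window is final dose + 56 ± 3 days. The final dose is on day 323 (Q2W) or day 330 (QW).

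- Q2W: 323 + 53 = 376 to 323 + 59 = 382. Unassigned days: 341 to 375, that is 35 days.
- QW: 330 + 53 = 383 to 330 + 59 = 389. Unassigned days: 341 to 382, that is 42 days.

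The MaPS and COMPASS 31 tables have no follow-up row, so for them no later window exists. The SAP's note on merging windows with neighbouring visits gives no late limit for Week 48, because no treatment visit follows it.

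**Comparison with Week 24 (target 169) in the same tables.**

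- MaPS (156–211) and COMPASS 31 (128–211): 211 − 169 = 42 days late accepted.
- Chemistry/hematology, ECG and immunogenicity (128–253): 253 − 169 = 84 days late accepted.

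**Comparison with the protocol visit window.** 337 ± 2 gives days 335 to 339, so day 340 is one day beyond it.

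**Illustration of size (assumed lateness, not in the documents).** If 5% to 10% of Week 48 visits were 4 or more days late, 38 × 0.05 = 1.9 to 38 × 0.10 = 3.8, so about 2 to 4 participants would leave each Week 48 summary. At an unchanged SD, the half-width of a 95% CI is proportional to t/√n. Against n = 38 it widens by 2.9% at n = 36 and by 6.2% at n = 34.

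**The case against.** The strongest reply is that a visit 4 days late is already a protocol deviation, that day 340 gives a day of slack, and that a tight upper limit keeps Week 48 close to treatment. Protocol 4.3 cites maintained IgG reduction for at least 2 weeks after the last dose. For Q2W participants that reaches 323 + 14 = day 337. This is a fair reason not to extend the window without limit, and a reason to leave PK and total IgG alone. It does not explain why the same tables accept values 42 or 84 days late at Week 24. Nor does deviation status remove anyone from the efficacy set: efficacy uses the FAS, and no per-protocol set is defined.

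The early side also matters less than its width suggests. No questionnaire is scheduled between Week 36 (day 253) and Week 48, and no chemistry, ECG or ADA sample between Weeks 24 and 48. Early values can therefore come only from unscheduled or discontinuation visits, and an on-time value displaces them under the nearest-to-target rule. That stands.

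A reader might go further and infer that late data are lost to the analysis altogether, or that Week 48 is the only ADA sample after Week 24. The documents do not support either:

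- Worst-case laboratory and ECG tables take all postbaseline values (SAP 6.4).
- ADA classification uses the highest postbaseline status without tying it to a visit (SAP 15.4, Table E).
- ADA and physical examination are also scheduled at the safety follow-up visit (Protocol Table 2).
- AE summaries are not windowed by visit.

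A reader might also infer that all the windows share one asymmetric pattern. The generic window is symmetric, and PROMIS Cognition does not close on day 340.

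**Conclusion.** The point holds for the Week 48 by-visit summaries, mainly the questionnaires. As written, a MaPS or COMPASS 31 value from day 341 onward has no window, while one up to 41 days early can count. For chemistry/hematology, physical examination, immunogenicity and ECG the early allowance is 83 days. The gap contradicts the SAP's own statement that all assessments are allocated. The PROMIS Cognition row needs correcting whatever is decided about lateness.

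The consequence is moderate. The study is descriptive and tests no hypothesis, and the loss requires a visit outside the protocol window. The illustrative 2 to 4 participants and 3% to 6% wider interval rest wholly on an assumed lateness rate. A systematic tilt of the Week 48 results towards discontinuation-visit values is possible but is not shown by the documents. The limits, the gap and the contrast with Week 24 follow from the printed tables alone.

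**What to change.** In SAP 6.3:

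1. Extend the upper limit of the Week 48 window for questionnaires, chemistry/hematology, physical examination, ECG and ADA, for example to day 351 (337 + 14). Keep the nearest-to-target rule.
2. Exclude records from the nominal safety follow-up visit. This matters for participants who stop early: a last dose on day 292 puts that visit on days 345 to 351.
3. Keep day 340 for PK and total IgG, where time since dose drives the value.
4. Correct the PROMIS Cognition upper limit in the same edit, and confirm that the PGI-S/PGI-C/PROMIS Fatigue row has limits.
5. Reconcile the two allocation sentences by saying what happens to a value that falls in no window.
6. Footnote values after day 340 with days since last dose, and show the Week 48 questionnaire summaries with and without them.

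The cost is SAP wording, one limit per table and one extra display. A late value could be 351 − 323 = 28 days after the last Q2W dose, or 351 − 330 = 21 days on QW, against 14 and 7 days when on time; item 6 makes that visible. ADA and PK samples drawn together would have different Week 48 limits, which also needs a footnote. The change does not remove early-discontinuation values from Week 48; if that is wanted, it is a separate decision.

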### Non-efficacy Analysis Visit Definition

	Target Day Assigned Study Day (Inclusive)		Day (Inclusive)	Week Assigned
		From	То	
Treatment	1		1ª	Baseline
	8	1 b	11	Week 1
	15	12	18	Week 2
	22	19	25	Week 3
•	29	26	32	Week 4
•	36	33	39	Week 5
	43	40	46	Week 6
	50	47	53	Week 7
	57	54	60	Week 8
	57 + (x*7)	57 + (x*7) - 3	57 + (x*7) + 3	Week 8+x °
Safety Follow- up	Final dose + 56 days	(Final dose + 56 days ) - 3 days	(Final dose + 56 days ) + 3 days	Week xx+ 56 days

<sup>a Last available non-missing measurement from the parent study 2104.

Note: After treatment period ends, safety follow-up will be of approximately 8 weeks (56 days  $\pm$  3 days) . Some parameters which are not collected at every visits, visit window will be combined (by extending window with previous or subsequent visits).

Document: BIOSdata\argenx\Efgartigimod\HAB40220\Biostatistics\Documentation\SAP

Author: Version Number: 1.0

Version Date: 03 June 2024

Template No.: CS\_TP\_BS016 Revision 7 Reference: CS\_WI\_BS005

<sup>b Post baseline visit Day 1.

c considers value of x, starting from 1 to up until 40 to get visit windows for Week 9 to Week 48.

Page 19 of 54

### Serum Checmistry and hematology, Physical examination, Analysis Visit Definition

	Target Day	Assigned Study Day (Inclusive)		Week Assigned
		From	То	
Treatment	1		1 a	Baseline
	29	1 b	57	Week 4
	85	58	127	Week 12
	169	128	253	Week 24
	337	254	340	Week 48
Safety Follow- up	Final dose + 56 days	(Final dose + 56 days ) - 3 days	(Final dose + 56 days ) + 3 days	Week xx+ 56 days

<sup>a Last available non-missing measurement from the parent study 2104b Post baseline visit Day 1.

### Immunogenicity, Analysis Visit Definition

	Target Day Assigned Study Day (Inclusive)		ay (Inclusive)	Week Assigned
		From	То	
Treatment	1		1ª	Baseline
	8	1 b	18	Week 1
	29	19	57	Week 4
	85	58	127	Week 12
	169	128	253	Week 24
	337	254	340	Week 48
Safety Follow- up	Final dose + 56 days	(Final dose + 56 days) - 3 days	(Final dose + 56 days ) + 3 days	Week xx+ 56 days

<sup>a Last available non-missing measurement from the parent study 2104b Post baseline visit Day 1.

### ECG, Analysis Visit Definition

Target Day	Assigned Study D	ay (Inclusive)	Week Assigned
	From	То	

Document: BIOSdata\argenx\Efgartigimod\HAB40220\Biostatistics\Documentation\SAP

Author: Version Number: 1.0

> Version Date: 03 June 2024

Template No.: CS\_TP\_BS016 Revision 7 Reference: CS\_WI\_BS005

Page 20 of 54

Treatment	1		1 a	Baseline
	85	1 b	127	Week 12
	169	128	253	Week 24
	337	254	340	Week 48
Safety Follow- up	Final dose + 56 days	•	(Final dose + 56 days ) + 3 days	Week xx+ 56 days

<sup>a Last available non-missing measurement from the parent study 2104b Post baseline visit Day 1.

### **Efficacy Analysis Visit Definition**

For MAPS efficacy assessments, the following window will be considered:

Target Day	Assigned Str	ıdy Day (Inclusive)	Week Assigned
	From	То	
1		1	Baseline
15	2	22	Week 2
29	23	36	Week 4
43	37	50	Week 6
57	51	64	Week 8
71	65	78	Week 10
85	79	99	Week 12
113	100	127	Week 16
141	128	155	Week 20
169	156	211	Week 24
253	212	295	Week 36
337	296	340	Week 48

Last available non-missing measurement from the parent study 2104

For COMPAS efficacy assessments, the following window will be considered:

Target Day	Assigned Study Day (Inclusive)	
------------	--------------------------------	--

Document: BIOSdata\argenx\Efgartigimod\HAB40220\Biostatistics\Documentation\SAP

Author: Version Number: 1.0

Version Date: 03 June 2024

Template No.: CS\_TP\_BS016 Revision 7 Reference: CS\_WI\_BS005

	From	То	Week Assigned
1		1	Baseline
15	2	22	Week 2
29	23	43	Week 4
57	44	71	Week 8
85	72	127	Week 12
169	128	211	Week 24
253	212	295	Week 36
337	296	340	Week 48

Last available non-missing measurement from the parent study 2104

For PGI-S, PGI-C and PROMIS Fatigue efficacy assessments, the following window will be considered:

Target Day	Assigned St	udy Day (Inclusive)	Week Assigned
	From	To	
1		1	Baseline
15	2	22	Week 2
29	23	57	Week 4
85	58	106	Week 12
169	149	178	Week 24
337			Week 48

Last available non-missing measurement from the parent study 2104

For PROMIS Cognition efficacy assessments, the following window will be considered:

Target Day	Assigned Study Day (Inclusive)		Week Assigned
	From	To	
1		1	Baseline
29	2	57	Week 4
85	58	127	Week 12
169	128	253	Week 24

Document: BIOSdata\argenx\Efgartigimod\HAB40220\Biostatistics\Documentation\SAP

Author: Version Number: 1.0

Version Date: 03 June 2024

Template No.: CS\_TP\_BS016 Revision 7 Reference: CS\_WI\_BS005

Page 22 of 54

337	254	240	Week 48
-----	-----	-----	---------

Last available non-missing measurement from the parent study 2104

Target Day	Assigned Study Day (Inclusive)		Week Assigned
	From	То	
1		1ª	Baseline
85	1 b	127	Week 12
169	128	253	Week 24
337	254	340	Week 48

<sup>a Last available non-missing measurement from the parent study 2104

Subject who permanently discontinue the treatment, assessment (COMPASS 31, MaPs, PGI-S and PGI-C, PROMIS, Exit Interview, ) will be collected at IMP discontinued visit which will be performed at next scheduled visit after discontinuation: EDV visits will be performed within 7 days of last contact with participant for those subjects who discontinue study permanently.

Per parameter and analysis window, the non-missing value closest to the target day will be used in the analysis. If more than one non-missing value is located at the same distance from the target day, then the one latest in time will be selected for analysis. The value latest in time will be identified using, in order of preference, the assessment time, the visit label, or group identifier (if applicable). Windowing will be applied to the data prior to any missing data calculations. Questionnaire Total scores and other assessments closest to the target date will be considered for questionnaires.

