## 15. SECONDARY ANALYSIS

## 15.1. Efficacy Variables & Derivations

The efficacy variables are:

- Change from baseline to week 24 and week 48 in the Composite Autonomic Symptom Score 31 (COMPASS 31, modified)
- Change from baseline to week 24 and week 48 in the Malmö POTS Symptom Score (MaPS)
- Change from baseline to week 24 and week 48 in the Patient Global Impression of Severity (PGI-S)
- Patient Global Impression of Change (PGI-C) at week 24 and week 48
- Change from baseline to week 24 and 48 in the Patient-Reported Outcomes Measurement Information System (PROMIS) Fatigue Short Form 8a
- Change from baseline to week 24 and 48 in the PROMIS Cognitive Function Short Form 6a

For analyses of change from baseline, the baseline is defined as the latest measurement prior to enrollment in the OLE study. Efficacy endpoints will be analyzed using the FAS for IA and FPA. No estimands have been defined for this study.

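### The PROMIS Cognition Week 48 window runs from day 254 to day 240 and so contains no day; the PGI-S, PGI-C and PROMIS Fatigue windows leave days 107–148 in no visit

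*SAP*

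**What the plan says.** SAP 6.3 states two allocation rules: "All assessments, including unscheduled assessments, will be allocated to analysis visit window", and "Allocations of assessments will be performed using their relative day and only for the scheduled visit windows". Within a window, "Per parameter and analysis window, the non-missing value closest to the target day will be used in the analysis".

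Two of the efficacy tables that follow matter here. One is introduced by "For PROMIS Cognition efficacy assessments, the following window will be considered", the other by "For PGI-S, PGI-C and PROMIS Fatigue efficacy assessments, the following window will be considered". Their post-baseline rows are:

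| Visit (target day) | PROMIS Cognition | PGI-S, PGI-C, PROMIS Fatigue |
|---|---|---|
| Week 2 (15) | not collected | 2–22 |
| Week 4 (29) | 2–57 | 23–57 |
| Week 12 (85) | 58–127 | 58–106 |
| Week 24 (169) | 128–253 | 149–178 |
| Week 48 (337) | 254–240 | no limits in the supplied text |

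SAP 15.1 lists "Change from baseline to week 24 and 48 in the PROMIS Cognitive Function Short Form 6a" among the efficacy variables, and protocol Table 3 names it as a secondary endpoint. Protocol Table 1 schedules PROMIS Cognition at Week 48, day 337 ± 2. Protocol Table 2 also collects all these questionnaires at the IMP discontinuation visit and the early discontinuation visit. For the former, the SAP says the questionnaires "will be collected at IMP discontinued visit which will be performed at next scheduled visit after discontinuation".

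**The concern.** A window that starts at day 254 and ends at day 240 cannot hold an observation. Because allocation is by study day and only to the scheduled visit windows, a programmer who follows the SAP exactly has no PROMIS Cognition value at Week 48, one of the two time points that define the endpoint.

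The second table has a hole between Week 12 and Week 24, against the statement that every assessment is allocated. An off-schedule visit in that hole is handled inconsistently across instruments. On days 128–148, which include the nominal days of Weeks 19, 20 and 21 (134, 141, 148), PROMIS Cognition and COMPASS 31 go to Week 24, while PGI-S, PGI-C and PROMIS Fatigue from the same visit go nowhere.

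**Working it through.** **1. Coverage of the printed windows.** Each study day from 2 to 340 was mapped to the windows in SAP 6.3.

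- PROMIS Cognition: 254 ≤ day ≤ 240 is never true. Days 254–340 are unassigned (340 − 254 + 1 = 87 days), including the scheduled visit days 335–339.
- PGI-S, PGI-C, PROMIS Fatigue: days 107–148 are unassigned (148 − 107 + 1 = 42 days). If the Week 48 cells really are blank, days 179–340 are unassigned too (162 days).
- MaPS and COMPASS 31: no unassigned day.

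**2. The convention behind the tables.** In the MaPS and COMPASS 31 tables every cut point is the midpoint of adjacent target days, and the last window ends at 337 + 3 = 340. For PROMIS Cognition the same rule gives:

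- (29 + 85)/2 = 57
- (85 + 169)/2 = 127
- (169 + 337)/2 = 253
- last day 337 + 3 = 340

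This reproduces every printed PROMIS Cognition limit except 240.

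**3. Other Week 48 upper limits in SAP 6.3.** The non-efficacy formula with x = 40 gives 57 + 40 × 7 + 3 = 340. The chemistry/hematology/physical examination, immunogenicity, ECG, MaPS, COMPASS 31 and final efficacy tables all print 340. That is seven of seven.

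**4. Source of the gap.** The limits 106 and 149 fit the midpoint rule around a Week 18 visit (day 127): (85 + 127)/2 = 106, and (127 + 169)/2 = 148, so Week 24 would start at 149. Days 107–148 are therefore exactly a Week 18 window. Protocol Table 1 has a Week 18 column but collects none of these three instruments there. The Week 24 upper limit of 178 fits neither candidate midpoint: (169 + 253)/2 = 211 or (169 + 337)/2 = 253.

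**5. Size.** The documents expect about 38 participants and give no discontinuation rate. Two assumptions are needed: 70–90% reach Week 48; and 10–30% (3.8 to 11.4 participants) have one discontinuation visit, spread evenly over the 339 days from 2 to 340, with no later questionnaire in the same window.

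- PROMIS Cognition, scheduled Week 48 values lost if the row is applied literally: 38 × 0.7 = 26.6 to 38 × 0.9 = 34.2.
- PROMIS Cognition, off-schedule values on days 254–340: 3.8 × 87/339 = 0.98 to 11.4 × 87/339 = 2.93.
- PGI-S, PGI-C, PROMIS Fatigue: under repaired windows, a value on days 107–127 would normally lose to the day 85 value, and one on days 179–253 to the day 169 value. Only days 128–148 (21 days) count: 3.8 × 21/339 = 0.24 to 11.4 × 21/339 = 0.71.
- The same three instruments if their Week 48 limits are truly blank: 21 + 87 = 108 days, giving 3.8 × 108/339 = 1.21 to 11.4 × 108/339 = 3.63 off-schedule values. Scheduled Week 48 values would also have no window.

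The off-schedule figures are upper figures, because a later scheduled value in the same window would replace the discontinuation value.

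**The case against.** **The 240 may be a reading error.** The row stands alone after a page break, so a misread digit is possible. If it is genuine, the correction is obvious and no competent programmer would deliver an empty Week 48 result. Both points are fair, and the 27–34 figure is the literal reading rather than a forecast. But the repair would then be an undocumented departure from the SAP. The error may also be less visible than it seems: SAP 7.2 shows only analysis visits with at least 10 participants, so an empty Week 48 would drop out of the by-visit table.

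**The gap has an explanation.** Its limits are those of a Week 18 window, which suggests a row removed or lost without rejoining its neighbours. That accounts for the gap but does not close it, because none of these questionnaires is scheduled at Week 18.

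**SAP 6.3 allows windows to be merged.** For parameters not collected at every visit, the "visit window will be combined (by extending window with previous or subsequent visits"). The note stands under the non-efficacy table and sets no limits. The efficacy tables print their own, and merging cannot repair an inverted window.

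**The gap barely matters.** This largely stands. If IMP discontinuation visits fall on the next scheduled questionnaire visit, they mostly avoid the gap. Protocol Table 2 instead puts that visit within 7 days of permanent discontinuation, and early discontinuation visits within 7 days of last contact, so some could still fall in it. The even-spread calculation shows only the order of magnitude.

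**Conclusion.** The point holds on the printed numbers. The PROMIS Cognition Week 48 window is empty as written, and a literal application removes the Week 48 result of a named secondary endpoint: about 27–34 scheduled values, at an assumed 70–90% retention of about 38 participants. The intended limit of 340 is hardly in doubt.

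The hole at days 107–148 contradicts the SAP's own allocation rule but affects about 0.2–0.7 participants, at an assumed 10–30% discontinuation. Scheduled visits through Week 24 are unaffected for all instruments.

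The missing Week 48 limits for PGI-S, PGI-C and PROMIS Fatigue are a query only, since they may have been lost in text extraction. The analysis is descriptive, so no test or error rate is involved. This should be corrected, but it does not threaten the study.

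**What to change.** - **Check first.** Compare the 240 and the apparently blank Week 48 cells with the source PDF, and ask the sponsor whether a Week 18 row was dropped from the shared table.
- **PROMIS Cognition.** Set Week 48 to days 254–340. This covers the target day and leaves no gap over days 2–340.
- **PGI-S, PGI-C, PROMIS Fatigue.** Set Week 12 to days 58–127, Week 24 to days 128–253 and Week 48 to days 254–340. These are the midpoints for targets 85, 169 and 337. The SAP already prints all three windows in its chemistry/hematology and immunogenicity tables, and the PROMIS Cognition table has the same Week 12 and Week 24 windows.

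The sponsor should confirm the limits in writing. The cost is a SAP correction and an updated programming specification; data collection does not change.
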